8.2 Classification of Adverse Events

8.2.1 Assigning Severity Rating for Adverse Events

8.2.1.1 Criteria for Determining Adverse Event Severity

The Investigator will make an assessment of the severity of each AE and SAE according to the National Cancer Institute CTCAE, v. 5.0, 2017. For terms not specified with the CTCAE, the criteria in Table 5 should be used to determine the grade severity.

Table 5: Criteria for Determining the Grade/Severity of Adverse Event Terms Not Specified by the National Cancer Institute CTCAE

Grade	Criteria
1	Mild; asymptomatic or mild symptoms, clinical or diagnostic observations only; intervention not indicated
2	Moderate; minimal, local, or noninvasive intervention indicated; limiting age-appropriate instrumental activities of daily living ^a
3	Severe or medically significant but not immediately life-threatening; hospitalization or prolongation of hospitalization indicated; disabling; limiting self-care activities of daily living ^b
4	Life threatening consequences; urgent intervention indicated
5	Death related to adverse event

a. Instrumental activities of daily living refer to preparing meals, shopping for groceries or clothes, using the telephone, managing money, etc.

b. Self-care activities of daily living refer to bathing, dressing and undressing, feeding self, using the toilet, taking medications, and not bedridden.

CTCAE = Common Terminology Criteria for Adverse Events.

AE severity should be recorded in the appropriate section of the AE CRF and in the subject's source documents.

8.2.1.2 Toxicity Management Criteria

8.2.1.2.1 Grade 1 or Grade 2 Adverse Event

Subjects who develop a Grade 1 or Grade 2 AE may continue investigational product at the discretion of the Investigator. Subjects who choose to withdraw from study due to a Grade 1 or 2 AE should have study withdrawal/early termination evaluations completed.

8.2.1.2.2 Grade 3 Adverse Event

Subjects who develop a Grade 3 AE should be managed as follows:

- If the Investigator has compelling evidence that the Grade 3 AE has not been caused by investigational product, then dosing may continue after discussion with the Medical Monitor.
- Subjects who develop a Grade 3 AE that the Investigator considers related to investigational product should have the investigational product discontinued. Subjects experiencing Grade 3 AEs requiring permanent discontinuation of investigational product should be followed weekly until resolution or stability of the AE and encouraged to have withdrawal study evaluations completed.

8.2.1.2.3 Grade 4 Adverse Event

Subjects who develop a Grade 4 AE should have investigational product permanently discontinued.

Subjects experiencing Grade 4 AEs requiring permanent discontinuation of investigational product should be followed weekly until resolution or stability of the AE and encouraged to have withdrawal study evaluations completed.

8.2.1.2.4 Folliculitis

Subjects using tapinarof topically may experience folliculitis. The majority of these events are mild or moderate and do not require intervention or interruption in study drug use. On close inspection, the morphology is similar to that of keratosis pilaris suggesting that the potential mechanism may be increased follicular cornification with subsequent follicular plugging. Importantly, AhR regulates the epidermal differentiation complex and tapinarof has been shown to repair the skin barrier through activation of stratum corneum components including fillagrin, hornerin and involucrin. This latter point suggests that the keratosis pilaris-like reaction may be an on-target effect associated with a therapeutic response to tapinarof cream.

While the majority of events have not required nor resulted in the need for intervention, several approaches can be employed to manage those patients with folliculitis who may be symptomatic including temporary interruption of study drug use at sites of folliculitis and/or the local application to affected areas of topical keratolytics such as 12% lactic acid lotion or 5-10% urea creams or lotions.

8.2.1.2.5 Other Management Criteria:

The Medical Monitor should be notified if any of the following occur:

- Severe signs or symptoms, or significant changes in any of the safety assessments, that put the safety of the subject at risk (e.g., laboratory tests or vital signs, etc.) as judged by the Investigator.

8.2.2 Assigning Causal Relationship to Study Drug

The Principal Investigator or sub-Investigator is to make the causality assessment. The reasonable possibility of the relationship of an AE to study drug is to be assessed with careful medical consideration at the time of evaluation of an AE. The following definitions are to be used for the relationship of the AE to study drug:

- **Related:** A clinical event, including laboratory test abnormality, with a temporal relationship to study drug administration that makes a causal relationship plausible, unlikely attributed to concurrent disease or other drugs or chemicals, and that follows a clinically reasonable response on re-administration (rechallenge) or withdrawal (dechallenge), although information on drug withdrawal may be lacking or unclear.
- **Not related:** A clinical event, including laboratory test abnormality, with a temporal relationship to study drug administration that makes a causal relationship improbable and/or in which other drugs, chemicals, or underlying disease provide a plausible explanation.

Any AEs /SAEs assessed as related to study participation (e.g., protocol-mandated procedures, invasive tests, or change in existing therapy) or related to study drug will be recorded from the time a subject consented to participate in the study up to and including any follow-up contact.

All AEs, whether related to study drug or not, must be fully and completely documented on the AE page of the CRF and in the subject's clinical record. In the event a subject is withdrawn from the study because of an AE, the primary reason for withdrawal (i.e., due to an AE) must be recorded on the CRF as such.

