8.1 Adverse Events, Serious Adverse Events, and Adverse Events of Special Interest

The Investigator or site staff is responsible for detecting, documenting, and reporting events that meet the definition of an AE, SAE, or AESIs. At each visit/contact, subjects should be questioned in a general way so as not to introduce bias in detecting AEs and/or SAEs. Open-ended and non-leading verbal questioning of the subject is the preferred method to inquire about AE occurrence.

Investigators are not obligated to actively seek AEs or SAEs in former study subjects. However, if the Investigator learns of any SAE, including a death, at any time after a subject has been discharged from the study, and he/she considers the event reasonably related to the study drug or study participation, the Investigator should promptly notify the Sponsor.

A narrative will be written and included in the Clinical Study Report for all SAEs and AESIs, and for all AEs that lead to study discontinuation.

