8.1.3 Adverse Events of Special Interest

In prior clinical studies, contact dermatitis, folliculitis, and headache have been identified as AEs of particular clinical importance and will be reported as AESIs in this study whether or not the AE is considered related to study drug.

In each case study drug may be continued or discontinued, based on Investigator judgment, and may be restarted when the event resolves. In addition, the following information must be collected for each of these AESIs:

Contact Dermatitis

The study site should collect location, duration, size, associated symptoms (itching, burning, pain), severity (mild, moderate, severe), time to onset, and photograph the affected site (if possible). If the subject or caregiver contacts the study site to report significant skin irritation at or near the site of study drug application between study visits, the subject should be brought in for an unscheduled visit, if possible.

Headache

The study site should collect duration, severity (mild, moderate, severe), time to onset, and location (e.g., frontal, temporal, occipital, diffuse).

Follicular Event

The study site should collect the location, duration, size, associated signs and symptoms (itching, burning, pain, erythema), severity (mild, moderate, severe), describe morphology [scale (keratotic/cornified) or no scale (non-keratotic/non-cornified)], time to onset, and photograph the affected site (if possible). Additional information regarding management of folliculitis is provided in Section 8.2.1.2.4.

In particular, the term 'folliculitis' may not correctly describe the morphology of the observed local follicular events as these appear to be more consistent with a keratoses pilaris-like follicular based papule. Tapinarof upregulates components of the stratum corneum, including involucrin, hornerin, and filaggrin and increased cornification at, and subsequent mechanical occlusion of, the follicular ostia has been suggested to be a potentially on target mechanism by which these lesions may develop in some individuals treated with tapinarof cream. Additional morphologic description will help to more fully and appropriately characterize these follicular events.

Possible descriptors include, but are not limited to:

- Folliculitis
 - Non-inflammatory
 - Inflammatory
- Milia
 - Non-inflammatory
 - Inflammatory
- Keratosis pilaris

- Non-inflammatory
- Inflammatory

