8.5 Pregnancy Management and Reporting

Any female subject who becomes pregnant during the study will be withdrawn. Details will be collected for all pregnancies in female subjects and female partners of male subjects that begin after the start of dosing and through the Follow-up visit. Pregnancy is not automatically considered an AE.

If a pregnancy is reported, then the Investigator should complete a Pregnancy Report Form and submit via email or fax to the Pregnancy Reporting Contact for which contact information can be found on the [Medical Monitor / Sponsor Information Page](#) of this protocol, within 2 weeks of learning of the pregnancy. The subject will also be followed to determine the outcome of the pregnancy. Information on the status of the mother and child will be forwarded to the Sponsor. Generally, follow-up will be no longer than 6 to 8 weeks following the estimated delivery date. Any premature termination of the pregnancy will be reported.

Any SAE occurring in association with a pregnancy brought to the Investigator's attention after the subject has completed the study and considered by the Investigator as possibly related to the study drug must be promptly reported to the Sponsor or the Sponsor's representative.

The Investigator must attempt to collect pregnancy information on any female partners of male study subjects who become pregnant while the subject is enrolled in the study. Pregnancy information must be reported to the Sponsor or the Sponsor's representative as described above. The partner will also be followed to determine the outcome of the pregnancy. Information on the status of the mother and child will be forwarded to Sponsor or the Sponsor's representative. Generally, follow-up will be no longer than 6 to 8 weeks following the estimated delivery date. Any premature termination of the pregnancy will be reported on the Pregnancy Report Form.

9 Data Management

For this study, subject data will be entered into the Sponsor-defined CRFs, transmitted electronically to the Sponsor or designee, and combined with data provided from other sources in a validated data system.

Management of clinical data will be performed in accordance with applicable Sponsor standards and data cleaning procedures will be used to ensure the integrity of the data, e.g., errors will be corrected, and inconsistencies queried in the data.

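### The two causality definitions in Protocol 8.2.2 do not implement the reasonable-possibility standard that the section sets, so AEs with mixed causes generally fall under Not related

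*Protocol*

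**What the plan says.** Protocol 8.2.2 sets the standard in its lead-in: "The reasonable possibility of the relationship of an AE to study drug is to be assessed with careful medical consideration". It then makes two definitions mandatory: "The following definitions are to be used for the relationship of the AE to study drug".

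- **Related** describes an event whose timing "makes a causal relationship plausible, unlikely attributed to concurrent disease or other drugs or chemicals". It adds a reasonable response to rechallenge or withdrawal, but softens this: "although information on drug withdrawal may be lacking or unclear".
- **Not related** describes an event whose timing "makes a causal relationship improbable and/or in which other drugs, chemicals, or underlying disease provide a plausible explanation".

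There is no third category. SAP 13.2 tabulates causality at the same two levels. Its only rule on relationship is that a missing entry counts as related.

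**The concern.** The lead-in and the definitions ask different questions. The lead-in asks whether drug causation is reasonably possible. The definitions ask whether anything else could explain the event: Related needs alternatives to be unlikely, and the and/or in Not related lets one plausible alternative decide the matter. An event can have a reasonable possibility of drug causation and still meet the Not related definition.

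This matters for a topical drug in a skin disease, where underlying AD can be an alternative for an application-site event. The follicular AESI shows how it could arise. Protocol 8.1.3 says of these events that "these appear to be more consistent with a keratoses pilaris-like follicular based papule", and 8.2.1.2.4 suggests that the reaction may be an on-target drug effect. Appendix 1 lists keratosis pilaris among the minor diagnostic features of AD. For some of these events both explanations could be plausible.

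At stake are the outputs that select or classify by the label. With about 60 sites, some may follow the lead-in and others the definitions, so that one label carries two meanings. The SAP's conservative rule does not help: a blank relationship counts as related, while an event with a recognised plausible drug cause may not.

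**Working it through.** The plan gives no figure to reproduce. The check is one of logic, followed by a count of the outputs affected and an illustrative bound.

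**Step 1. Apply both definitions to each case** (inputs: the two definitions in 8.2.2). The rechallenge or withdrawal condition is taken as met or uninformative.

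| Drug cause | Alternative cause | Meets Related? | Meets Not related? |
|---|---|---|---|
| Plausible | Not plausible | Yes | No |
| Plausible | Plausible, and not unlikely | No | Yes |
| Plausible | Plausible but unlikely | Yes | Yes |
| Improbable | Plausible | No | Yes |
| Improbable | Not plausible | No | Yes |

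Row 2 is the defect: a plausible drug cause exists, yet only Not related is met. Row 3 is an ambiguity: both definitions are met and the text does not say which prevails. Nothing elsewhere in the protocol or SAP resolves either row.

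**Step 2. Count the outputs in SAP 13.2 that the label selects or classifies.**

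- 2 of the 12 TEAE incidence rows (treatment-related TEAE; treatment-related serious TEAE)
- 2 SOC/PT tables (treatment-related TEAEs; TEAEs by maximum causality)
- 1 listing (TEAEs related to study drug)
- 3 AESI causality summaries (contact dermatitis, follicular event, headache)

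2 + 2 + 1 + 3 = 8. The listing of all AEs also shows the label but is not selected by it.

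**Step 3. Bound the undercount.** Let r be the share of subjects with a drug-plausible AE, and m the share of those whose event also has a plausible alternative. Assume one such event per subject. If every mixed event is labelled Not related, the labelled rate is r(1 − m). If none is, it is r. The relative loss is therefore at most m, whatever r is.

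The documents give neither r nor m. Assume r = 0.20 among the 267 planned tapinarof subjects: 0.20 × 267 = 53.4 subjects.

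| Assumed m | Worst-case labelled rate | Worst-case subjects (of 53.4) |
|---|---|---|
| 0.1 | 0.20 × 0.9 = 18% | 48.1 |
| 0.3 | 0.20 × 0.7 = 14% | 37.4 |
| 0.5 | 0.20 × 0.5 = 10% | 26.7 |

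Assume r = 0.10 on vehicle and the same m in both arms. The vehicle rates become 9%, 7% and 5%. The ratio stays at 2.0, and the difference falls from 10 points to 9, 7 and 5. The constant ratio follows from assuming equal m; it is not a result. These are floors, because row 3 events may still be labelled Related.

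**Step 4. Check the withdrawal rules.** Protocol 4.6.1 has three mandatory criteria. Two use relatedness, and the Grade 3/4 one cites 8.2.2. But under 8.2.1.2.2 dosing may continue after a Grade 3 AE if there is compelling evidence against a drug cause and the Medical Monitor has been consulted, and a merely plausible alternative is not that. Under 8.2.1.2.3 a Grade 4 AE stops drug permanently, with no causality condition.

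**The case against.** The strongest reply is that trained investigators will use the judgment that the lead-in asks for. Part of this stands. A reader might infer that every mixed-cause AE must be labelled Not related; row 3 shows that this is too strong, and it is why the bound is a worst case. But the definitions are mandatory, and row 2 leaves no room for judgment. Nor does the text ask which explanation is more plausible.

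A reader might also infer that subjects with mixed-cause Grade 3 or 4 events would be kept on drug. The documents do not support that: 8.2.1.2.2 and 8.2.1.2.3 largely cover these cases, and 4.6 lets the Investigator stop treatment for safety at any time. What remains is a wording mismatch with 4.6.1.

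A third tempting reading is that follicular events as a class will be recorded as Not related. That does not follow either. Section 8.1.1 keeps expected disease signs and non-worsening conditions from being AEs. Sections 8.1.3 and 8.2.1.2.4 alert investigators to the suspected drug mechanism, and 8.1.3 asks for time to onset and morphology. Underlying disease could explain some events, not the class.

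It can also be said that the documents never define a reasonable possibility, so there is no reference against which to call the label biased. That limits any claim about size. It does not reconcile the lead-in with row 2. Softer wording elsewhere adds little: 8.1 covers SAEs learned of after discharge where "he/she considers the event reasonably related to the study drug or study participation", and 8.5 covers late pregnancy-associated SAEs "considered by the Investigator as possibly related to the study drug must be promptly reported". These are reporting triggers, not causality categories, and a wider net for late SAEs can coexist with a stricter in-study label.

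Finally, the consequence is modest. Causality is assigned under blind with one definition for both arms (5.3), and no formal safety comparison is made (10.4.3). This stands, and it sets the weight of the point.

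**Conclusion.** The point holds as wrong as written. The definitions in 8.2.2 do not deliver the standard stated in the same section, and they push mixed-cause AEs towards Not related. The likely effect is undercounting and inconsistent labelling across sites in eight descriptive outputs. The relative loss is at most m and cannot be estimated from the documents; the subject counts above rest wholly on assumed r and m, strict use of the text, and one event per subject.

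All-causality TEAE tables do not use the label. In-study SAEs are reported whatever the causality (8.4.1), and AESIs are captured whether or not related (8.1.3). The efficacy analyses do not depend on this wording. The text should be corrected, but the trial's main conclusions do not hang on it. Confidence is high on the wording and low on the size of the effect.

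**What to change.** In Protocol 8.2.2:

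- Define Related as a reasonable possibility that study drug caused or contributed to the event, even if another explanation is also plausible.
- Define Not related as no reasonable possibility of this.
- Delete the condition that alternatives be unlikely, and the stand-alone plausible-alternative clause.

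The SAP's two labels can stay. Changes to 4.6.1 or 8.2.1.2 are a separate matter and are not needed for this repair.

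The cost is a protocol amendment, with IRB/IEC approval before use and submission to regulators under local requirements (11.1.2, 11.2.1), plus site retraining. Somewhat more AEs will be labelled related. If the change comes after enrolment starts, the data will hold two standards, so record the effective date and state in the study report which definition applied to which events.

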8.3 Time Period and Frequency for Event Assessment and Follow-Up

8.3.1 Adverse Event Reporting

All AEs will be collected from the time of signed informed consent until the final visit.

Any AEs assessed as related to study participation (e.g., protocol-mandated procedures, invasive tests, or change in existing therapy) will be collected from the time a subject consented to participate in the study up to and including any follow-up contact.

All SAEs will be recorded in the CRF and reported to the Sponsor within 24 hours via email or phone (refer to [Medical Monitor / Sponsor Information Page](#) for contact information) (see Section 8.4).

8.3.2 Follow-Up of Adverse Events

After the initial AE/SAE report, the Investigator is required to proactively follow each subject at subsequent visits/contacts. All SAEs and nonserious AEs will be followed until resolution, until the condition stabilizes, until the event is otherwise explained, or if the subject is lost to follow-up.

The Investigator will assess the outcome of each AE using the following criteria:

- **Recovered/Resolved:** The event has improved or subject recuperated.
- **Recovered/Resolved with sequelae:** The subject has recuperated but retained pathological conditions resulting from the prior disease or injury.
- **Recovering/Resolving:** The event is improving.
- **Not recovered/Not resolved:** The event has not improved or subject recuperated.
- **Unknown:** The outcome of the event is not known, not observed, not recorded, or refused.
- **Fatal:** Termination of life as an outcome of the AE.

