1.3.3 Overall Benefit Risk

Taking into account the measures taken to minimize risk to subjects in this study, the potential risks identified in association with tapinarof are justified by the anticipated benefits that may be afforded to subjects with AD.

2 Objectives and Endpoints

The objectives and associated endpoints of the study are as follows:

Objectives	Associated Endpoint
Primary	
• To evaluate the efficacy of tapinarof cream, 1% QD compared with vehicle control in subjects with AD	• Proportion of subjects who have a validated Investigator Global Assessment in Atopic Dermatitis (vIGA-AD™) score of clear or almost clear (0 or 1) and at least a 2-grade reduction from Baseline at Week 8.
Secondary/Exploratory	
Secondary:
 
 • Proportion of subjects with $\geq 75\%$ improvement in EASI from Baseline at Week 8 • Mean change in %BSA affected from Baseline at Week 8 • Proportion of subjects with $\geq 90\%$ improvement in EASI from Baseline at Week 8 • Proportion of subjects ≥ 12 years old with a Baseline Peak Pruritus-Numeric Rating Scale (PP-NRS) score ≥ 4 who achieve ≥ 4-point reduction in the PP-NRS from Baseline at Week 8 
Exploratory:
 
• To evaluate the safety and tolerability of tapinarof cream, 1% QD in subjects with AD	
 • Incidence, frequency, and duration of TEAEs and serious adverse events (SAEs) • Change from Baseline in laboratory values • Change from Baseline in ECG parameters • Change from Baseline in vital signs • Mean Investigator-assessed local tolerability scale (LTS) scores by visit (overall and sensitive areas) • Mean subject (or caregiver)-assessed LTS scores by visit
• To describe the effect of tapinarof cream, 1% QD on AD symptom severity and the associated impact on daily activities and attitudes in subjects with AD	
 •  •  • 

Objectives	Associated Endpoint
	
● [REDACTED]● [REDACTED]
• To evaluate plasma concentrations of tapinarof in subjects with AD	
● Plasma concentration of tapinarof at Weeks 4 and 8

3 Study Design

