13.2 Adverse Events

All AE summaries will be restricted to TEAEs, which are defined as those AEs that occurred after dosing and those pre-existing AEs (prior to first application of study treatment) that worsened during the study. If it cannot be determined whether the AE is treatment emergent due to a partial onset date, then it will be counted as such. Verbatim terms in the eCRFs will be mapped to SOCs and PTs using MedDRA (Version 24.0). The one exception will be the summary of Any AE which will include AEs not considered treatment-emergent. The summary of Any AEs will be reported in the Overall Summary of Adverse Events.

For subjects not rolling over to the OL-LTE study, all reported AEs will be included in the Double-Blind phase summaries. For subjects rolling over to the OL-LTE study, all AEs with an onset date on or before the Week 8 visit date will be included in the Double-Blind phase summaries.

Imputation of start and end dates of AEs

To calculate duration of AEs, the following rules will be used where applicable to impute partial or completely missing start dates or end dates:

• If only the day is missing for a start date, the 1st of the month will be imputed. If the new estimated date falls before the date of first dose, while the known month and year match the month and year of the first dose, the date of first dose will be used as the new estimated date. The AE will be considered as a treatment-emergent AE (TEAE).

- If only the day is missing for an end date, the last day of the month will be imputed. If the new estimated date falls after the date of last study visit, the date of last study visit will be used as the new estimated date. Last study visit is defined as the Week 8 visit for those who elect to participate in the OL-LTE study, or the Week 9 follow-up visit for those who fail to qualify for participation in the OL-LTE study, or who qualify to participate but ultimately elect not to enroll.
- If both the day and the month are missing for a start date or end date, no imputation will be used, and the duration will not be calculated. However, if the year of start is the same or greater than the year of the first dose date, the AE will be considered as a TEAE.
- If the start date or end date is completely missing, duration will not be calculated. However, an event with completely missing start date will be considered as a TEAE.

Imputation of missing relationship and/or missing severity

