At each level of summarization, a subject will be counted once if he/she reported one or more events. The severity of TEAEs and relationship to study drug will be summarized in a similar manner. For summaries of relationship to study drug, a subject will be classified according related or not related. For summaries of TEAE CTCAE grade, a subject will be classified according to the worst grade.

For treatment-emergent AESIs, summarization will be more extensive, reflecting the more detailed information collected. Information summarized will include number of events per subject, earliest onset day, duration (in days), causality, grade, and seriousness of AESIs, outcome, actions taken with study drug, assorted physical characteristics of the AESIs, and demographic/baseline characteristics and vIGA-ADTM status. Each type of AESI will be summarized separately. If a subject has more than one treatment-emergent occurrence of an AESI, the subject's maximum duration, highest levels of causality and seriousness, maximum grade and generally the most extreme level of each characteristic will be summarized. If an AESI is ongoing at time of study completion/discontinuation, it will not be included in the duration summary.

A Kaplan-Meier figure will be generated for each treatment-emergent AESI of time to first event. Subjects not experiencing the AESI will be censored at the date of study completion or discontinuation.

For purposes of CT.gov reporting, two additional summaries of AEs by SOC, PT and treatment group will be done as follows:

- including only PTs >= 1% (in either treatment group)
- including only PTs \geq 5% (in either treatment group)

Each of these two summaries will include a total row summarizing the number of subjects with at least one of the PTs that meet the corresponding threshold.

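### The AE outcome code Recovered/Resolved is met by improvement alone, so the share of AESIs reported as resolved can be overstated

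*Protocol*

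**What the plan says.** Protocol Section 8.3.2 lists six outcome codes. Three of them divide up events according to improvement:

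- *Recovered/Resolved*: "The event has improved or subject recuperated".
- *Recovering/Resolving*: "The event is improving".
- *Not recovered/Not resolved*: "The event has not improved or subject recuperated".

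The other three are *Recovered/Resolved with sequelae*, which requires recuperation with residual pathology, *Unknown* and *Fatal*.

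The same section sets the end of follow-up: "All SAEs and nonserious AEs will be followed until resolution, until the condition stabilizes, until the event is otherwise explained", or loss to follow-up.

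The codes feed the reporting. SAP Section 13.2 says of AESIs: "Information summarized will include number of events per subject, earliest onset day, duration (in days), causality, grade, and seriousness of AESIs, outcome". It also leaves out of the duration summary any AESI still ongoing when the subject completes or discontinues the study. Protocol Section 2 names duration of treatment-emergent and serious events among the safety endpoints.

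**The concern.** An outcome scale should let a reader separate events that are over from events that are not. Here both ends of the scale use improvement as the dividing line. The code for a completed recovery asks for less than the code for recovery with sequelae, which has no improvement alternative. A follicular event or contact dermatitis that goes from moderate to mild can be recorded as resolved while it is still there.

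At stake is the descriptive tolerability picture for contact dermatitis, follicular events and headache. These are the three prespecified AESIs in a study meant to support registration. If improved but persisting events are counted as resolved, the outcome table says something that the underlying events do not.

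**Working it through.** The plan gives no figure to reproduce on this point. The first check is one of logic, and the second tests direction only.

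**Step 1. Which codes fit which event, read literally.** *Unknown* and *Fatal* do not apply to any of these cases.

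| State of the event | Recovered/Resolved | With sequelae | Recovering/Resolving | Not recovered |
|---|---|---|---|---|
| Over, no residue | fits | no | no | no |
| Better than before, still improving | fits | no | fits | no |
| Better than before, then stable, still present | fits | no (no recuperation) | no (no longer improving) | no (it has improved) |
| Never better | no | no | no | fits |

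Row 2 is an overlap: two codes are open and the text does not choose between them. Row 3 is more serious, because the only code that fits is the one whose label says the event is over. Row 3 is also an event whose follow-up may end because it has stabilized, so that code may be its last.

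**Step 2. What the code feeds.** Outcome goes directly into the AESI summary. Duration is a separate matter. SAP Section 13.2 works from dates ("To calculate duration of AEs, the following rules will be used where applicable to impute partial or completely missing start dates or end dates") and does not name the outcome code as an input. Neither document says that *Recovered/Resolved* requires or sets an end date, or whether an AESI counts as ongoing because of its outcome code or because its end date is blank. The annotated CRF cited in SAP Section 2 might settle this, but it is not among the documents reviewed.

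**Step 3. Direction under the most extreme reading.** The assumptions, none of which comes from the plan, are:

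- onset uniform over Days 1 to 57, with observation to Day 64 for everyone;
- every event closed, with an end date, when it improves;
- ongoing events excluded from the duration summary;
- events counted singly, whereas the SAP takes the most extreme value per subject.

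*Case A: exponential durations with mean m, improvement at a fraction f of the true duration.* The share resolved on study is R(m) = 1 − (m/56) × (e^(−7/m) − e^(−63/m)). With closure at improvement, the mean becomes f × m.

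- m = 14, true resolution: 1 − 0.25 × (0.6065 − 0.0111) = 0.851.
- m = 14, f = 0.5, so R(7): 1 − 0.125 × (0.3679 − 0.0001) = 0.954.

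Mean summarized durations come from simulation with 400,000 events:

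| True mean (days) | Resolved: true | Resolved: f = 0.75 | Resolved: f = 0.5 | Mean duration (days): true | f = 0.75 | f = 0.5 |
|---|---|---|---|---|---|---|
| 7 | 95.4% | 97.5% | 99.2% | 6.3 | 4.9 | 3.4 |
| 14 | 85.1% | 90.4% | 95.4% | 10.5 | 8.7 | 6.3 |
| 28 | 66.3% | 74.9% | 85.1% | 14.7 | 13.1 | 10.5 |
| 56 | about 44% | 53.2% | 66.3% | 17.7 | 16.6 | 14.7 |

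*Case B: 60% short events (mean 5 days, closed correctly) and 40% that outlast the study but improve after 20 to 40 days (uniform).*

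- Truly resolved: 0.6 × [1 − (5/56) × 0.2466] = 0.6 × 0.978 = 58.7%.
- Persistent events that improve in time: 0.4 × (63 − 30)/56 = 23.6%, so the reported share is 58.7% + 23.6% = 82.3%.
- Mean recorded duration of those persistent events: [63 × 30 − (30² + 20²/12)]/33 = (1890 − 933.3)/33 = 29.0 days.
- Mean summarized duration rises from 4.7 days to (0.587 × 4.7 + 0.236 × 29.0)/0.823 = 11.7 days.

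The resolved share rose in every scenario. Summarized duration fell in Case A and rose in Case B, because persistent events that should have been excluded as ongoing now enter the summary.

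**The case against.** The strongest reply is that the labels speak for themselves. *Recovered/Resolved* is a completed state and *Recovering/Resolving* is one in progress, and an experienced investigator will put a half-healed rash under the second. For an event still improving, that stands: the text allows miscoding but does not direct it. It does not answer the plateaued event, for which the second code's own definition fails.

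A reader might also infer three stronger consequences. The documents do not support them.

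- **AE durations are shortened.** An individual duration shortens only if the site enters an end date at improvement. Nothing requires that, and Protocol Section 8.1.3 has sites collect AESI duration as an item of its own. Even if sites did so, excluding ongoing AESIs lets the summarized mean move either way, as Case B shows.
- **Follow-up ends early.** Protocol Sections 8.3.2 and 8.4.1 already allow follow-up to end at stabilization or when the event is otherwise explained. AEs are also recorded at every visit and phone contact. Little of any early stop could be put down to this definition.
- **The active arm is flattered.** The same wording applies to both arms under double blinding. If AESIs are more frequent on tapinarof, more of that arm's events are exposed to loose coding. But incidence, grade, causality and action taken do not depend on the outcome definition, and no formal safety comparison is planned.

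**Conclusion.** The definition is wrong as written. Improvement alone satisfies *Recovered/Resolved*, the code overlaps *Recovering/Resolving*, and an improved, stable, still-present event has nowhere else to go. The consequence that follows from the text is that the share of AESIs reported as resolved can be overstated. Distortion of durations, and of which AESIs enter the duration summary, is conditional on sites entering end dates at improvement, and its sign is not determined.

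The size cannot be derived. The documents give no AE durations, times to improvement or coding practice, and the figures above show direction under stated assumptions rather than an estimate. The effect is confined to descriptive safety reporting. The primary and secondary efficacy analyses and the power are unaffected.

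**What to change.** In Protocol Section 8.3.2 and the CRF completion guideline:

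1. Define *Recovered/Resolved* as the event having ended, or the condition having returned to its pre-event state, without sequelae. The last two words keep it distinct from *Recovered/Resolved with sequelae*.
2. Place any improvement short of that, including a plateau, under a not-yet-resolved category and treat it as ongoing. This means widening *Recovering/Resolving* beyond events that are actively improving, or widening *Not recovered/Not resolved*.
3. Reword *Not recovered/Not resolved* so that the codes neither overlap nor leave a gap.
4. State that an AE end date is entered only when the event is resolved, with or without sequelae, or fatal.

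SAP Section 13.2 should then say how an AESI is identified as ongoing for the duration summary.

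The cost is wording in the protocol and CRF guideline, one sentence in the SAP, and queries to sites on AESIs already closed as resolved. No change to design, sample size or efficacy analysis is needed.
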